#### 8.7.1.8.4 VITAL SIGNS

Descriptive statistics for vital signs parameters (ie, systolic and diastolic BP, pulse, respiratory rate, temperature, weight, and height) and changes from baseline will be presented by visit and treatment group.

Percentiles for BP values (only for subjects <18 years old) will also be summarized using a shift table of worst postbaseline from Baseline measurement by categories (<90th percentile,

90th to 95th percentile, 95th to  $\leq$ 99th percentile, systolic BP or diastolic BP  $>$ 99th percentile). See [Appendix 6](#) and [Appendix 7](#) for detail on percentiles.

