**Table 5 Schedule of Assessments in Study E7080-G000-230 – Randomization Phase**

Phase	Prerandomization		Randomization a (All cycles are 21 days in duration)																		
	Screening b	Baseline c	Treatment d																Off-Tx	Follow-up e	
Period	1	2	3	4	5	6	7	8	9	10	11	12	13	14	15	16	17	18+			
Visit	1	2	3	4	5	6	7	8	9	10	11	12	13	14	15	16	17	18+			
Cycle			Cycle 1			Cycle 2			Cycle 3			Cycle 4			Cycle 5			Cycle 6-X			
Day	-28 to -2	-1	1	8	15	1	8	15	1	8	15	1	8	15	1	8	15	1			
Procedures/Assessments																					
Informed consent	X																				
Inclusion/exclusion	X	X																			
Randomization (IVRS)			X																		
Demographic data	X																				
Medical/surgical history	X	X																			
Prior medication/ procedures	X	X																			
Pregnancy test f	X	X				X			X			X			X			X	X	X	X
Lansky play score/ Karnofsky PS g	X	X	X			X			X			X			X			X		X	
TNM Staging	X																				
Physical examination h	X	X	X		X	X		X	X			X			X			X	X	X	X
Vital signs i	X	X	X	X j	X	X		X	X			X			X			X	X	X	X
12-lead ECG k	X		X			X												X	X		
Echocardiogram l	X	Performed every 16±2 weeks following the first dose of study drug or sooner, if clinically indicated																X			
Clinical chemistry and hematology m	X	X			X	X		X	X			X			X			X	X	X	X
Urine dipstick testing n	X	X			X	X		X	X			X			X			X	X	X	X
PK blood samples o			X		X	X															
Study treatment p			Arm A: Combination of lenvatinib (QD) + ifosfamide + etoposide (Days 1-3 of Cycles 1-5 only) [based on BSA calculations at Day 1 of each Cycle]; after Cycle 5 subjects will receive lenvatinib alone. Arm B: Ifosfamide + etoposide (Days 1-3 of Cycles 1-5 only) [based on BSA calculations at Day 1 of each Cycle]																		

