- p. Subjects randomized to Arm A will continue to receive lenvatinib only after completion of 5 cycles with lenvatinib+ifosfamide+etoposide until progressive disease, unacceptable toxicity, subject request, study termination by the sponsor, subject noncompliance with safety or efficacy assessments, or withdrawal of consent. Subjects randomized to Arm B will be off-treatment after 5 cycles of ifosfamide+etoposide.
- q. All subjects who receive suspension formulation, with the exception of subjects using a nasogastric or gastrostomy tube, must complete the Palatability Questionnaire according to the Schedule of Assessments. If the subject is unable to complete the questionnaire this must be done by their parents or their legal guardian.
- r. **Screening:** Tumor assessments of the chest, abdomen, pelvis, and other areas of known disease or newly suspected disease should be performed within 28 days prior to C1D1. Scans of the abdomen, pelvis, and other areas of the body may be done with MRI instead of CT, but evaluation of the chest should be done with CT. CT scans should be performed with oral and iodinated IV contrast and MRI scans should be performed with IV gadolinium chelate.

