- t. Height will be assessed at the Baseline Visit, Day 1 of every 4 cycles during the Treatment Phase, at the Off-treatment Visit and every 3 months during the Post-treatment Follow-up. Proximal tibial growth plates x-rays should be conducted at baseline and at the Off-treatment Visit. If the growth plates are closed at baseline then the subject does not need a reassessment at the Off-treatment Visit. Tibial growth plate x-rays will be optional for Germany.
- u. Tanner Stage will be assessed at the Baseline Visit, at the Off-treatment Visit, and annually thereafter during the Post-treatment Follow-up.
- v. Blood samples will be collected only from subjects in Arm A at the Baseline Visit, C1D15, Day 1 of Cycles 2, 4, and 6, for assessment for blood serum sample to measure factors implicated in angiogenesis.
- w. An archival tumor sample from the most recent surgery or biopsy for identification of predictive biomarkers and pathology review may be collected from subjects in Arm A at any time during the study, unless no such material is available.
- x. Survival data will be collected every 3 months until death as per the protocol. All anticancer therapies will be collected.
- y. Concomitant medications will be recorded throughout the study and for 30 days after last dose. All anticancer therapy will be recorded until time of death or termination of Survival Follow-up.
- z. AEs will be recorded from the date of signed informed consent, throughout the study, and for 30 days after last dose. SAEs irrespective of relationship to study treatment must be reported as soon as possible but not later than 24 hours.

**Table 6** presents the Schedule of Procedures/Assessments for the Extension Phase of the study.

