### 8.7.1.8 Safety Analyses

All safety analyses will be performed on the Safety Analysis Set. Safety data, presented by treatment group, will be summarized on an “as treated” basis using descriptive statistics (eg, n, mean, standard deviation, median, minimum, maximum for continuous variables; n [%])

for categorical variables), as appropriate. Safety variables include TEAEs, clinical laboratory parameters, vital signs, 12-lead ECG results, Lansky play scores or Karnofsky performance scores, physical examination, height, closure of proximal tibial plates, and LVEF. Study Day 1 for all safety analyses will be defined as the date of the first dose of study drug.

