#### 8.7.1.8.6 OTHER SAFETY ANALYSES

Descriptive summary statistics for LVEF changes from baseline will be calculated and summarized.

The shift of worst postbaseline proteinuria from Baseline will be summarized.

Thyroid-stimulating hormone values will be summarized in 2 categories ( $\leq$ ULN and  $>$ ULN).

Lansky play scores or Karnofsky Performance Status score scores will be summarized by shifts from Baseline to worst postbaseline visit.

Radiographic findings of proximal tibial growth plates will be listed and analyzed if appropriate.

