### **Study Treatments**

Body surface area (BSA) will be used to determine the amount of study drugs administered, and must be calculated on Day 1 of each cycle based on the subject's current height and body weight. The dose should be rounded to the nearest whole number.

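### Section 8.7.1.8.4 summarises height by visit and arm across ages 2 to 25; add standardised height change in subjects under 18 at matched elapsed times

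*Protocol*

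**What the plan says.** Section 8.7.1.8.4 states the height summary: descriptive statistics for the vital signs, whose list closes "respiratory rate, temperature, weight, and height) and changes from baseline will be presented by visit and treatment group". The protocol file carries this section twice in the same words. Section 8.5.1.4.4 gives the unit of height as cm.

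The same section has one age-referenced output, for blood pressure: "Percentiles for BP values (only for subjects <18 years old) will also be summarized using a shift table". No section gives a height SDS, z-score, percentile or velocity, or splits height by age.

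Height is followed as a growth measure. Section 8.7.1.8 names it among the safety variables: "physical examination, height, closure of proximal tibial plates, and LVEF". For the growth plates, Section 8.7.1.8.6 commits only to this: "Radiographic findings of proximal tibial growth plates will be listed and analyzed if appropriate". Of these two, only height has a firm by-arm summary.

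Table 5 schedules height at baseline and on Day 1 of every fourth cycle on treatment, then "at the Off-treatment Visit and every 3 months during the Post-treatment Follow-up". On treatment length its footnote says: "Subjects randomized to Arm B will be off-treatment after 5 cycles of ifosfamide+etoposide". Arm A continues lenvatinib until progression or another stopping reason.

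**The concern.** The reason to measure height in this trial is to see whether adding lenvatinib slows growth in children. A table of centimetres over ages 2 to 25 is a weak way to see it, for two reasons.

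First, subjects aged 18 or over have little or no growth left. Including them pulls the mean change in both arms, and the difference between arms, towards zero.

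Second, treatment lasts five cycles in Arm B and is open-ended in Arm A. After Cycle 5, rows labelled by visit either hold one arm only or put very different elapsed times side by side. A child with more elapsed time has had longer to grow, so extra centimetres in long-treated Arm A children could hide slower growth on lenvatinib.

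At stake is how readable a descriptive safety table is. No test is attached to it.

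**Working it through.** The plan states no numerical figure on this point, so there is none to reproduce. The check is reading plus schedule arithmetic.

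**Inputs**
- About 72 subjects, at least 32 of them under 18 at consent (Synopsis, Study Design; Section 8.3), so up to 72 − 32 = 40 may be adults.
- 21-day cycles; chemotherapy on Days 1 to 3 of at most five cycles.
- Off-Treatment Visit within 30 days after the final dose (Section 8.1.2.1).
- Height on Day 1 of every fourth cycle, which from Cycle 5 gives Cycles 9, 13 and 17; then at the Off-Treatment Visit and every 3 months.
- Follow-up visits every 12 weeks (Table 5 footnote on follow-up).
- Safety Study Day 1 is the first dose (Section 8.7.1.8).

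**Dilution**

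Assume no adult growth and the same share of minors in each arm. The second assumption is reasonable because randomization is stratified at age 18. Then

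pooled difference ÷ difference in minors = minors ÷ 72

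| Minors | Share of effect shown |
|---|---|
| 32 (floor) | 32/72 = 44% |
| 40 | 40/72 = 56% |
| 48 | 48/72 = 67% |

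**Visit clock**

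Day 1 of cycle c falls on Day 21(c − 1) + 1.
- Cycle 5: Day 85 (Week 12), scheduled in both arms.
- Cycles 9, 13 and 17: Days 169, 253 and 337 (Weeks 24, 36 and 48), on treatment in Arm A only.

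**Off-Treatment Visit**
- Arm B, five cycles without delay: last dose on Day 84 + 3 = 87, so the visit falls on Days 88 to 117. The latest is 116 days after Day 1 (16.6 weeks).
- Arm A, treated through Cycle 18: 18 × 21 = Day 378 at the earliest, 377 days after Day 1 (53.9 weeks).
- Ratio: 377/116 = 3.25.

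**Can the arms be matched after Cycle 5?**

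Arm B follow-up heights, counted from an Off-Treatment Visit on Days 88 to 117:

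| Spacing | Days | After Arm A Cycle 9, 13, 17 Day 1 |
|---|---|---|
| 84 days | 172–201, 256–285, 340–369 | 3–32 days each |
| 91 days | 179–208, 270–299, 361–390 | 10–39, 17–46, 24–53 days |

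Windows on elapsed time can therefore pair the arms. A table by nominal visit puts the same heights in separate rows.

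**Matching up to Cycle 5**

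Besides the scheduled Cycle 5 height, BSA needs a current height in both arms. The Synopsis says of BSA: "and must be calculated on Day 1 of each cycle based on the subject's current height and body weight"; Table 5 repeats this for the control arm: "Arm B: Ifosfamide + etoposide (Days 1-3 of Cycles 1-5 only) [based on BSA calculations at Day 1 of each Cycle". The protocol does not say that each of these heights enters the CRF, so they should not be relied on.

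**How many remain later**

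With 32 minors, about 16 per arm. If height follow-up stopped at progression, the design assumptions in Section 8.7.2 would leave 16 × 25% = 4 in Arm B and 16 × 55% ≈ 9 in Arm A at 4 months, before the Week 24 window. The height footnote does not say that it stops there.

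**The case against.** The strongest objection is that this belongs in the SAP. Sections 8.7 and 8.7.1 defer detail to it, and a standardised score, an age split and analysis windows are ordinary SAP content. Section 8.7.1.8.4 neither calls the height values raw nor rules out a split, so the SAP could add all of this without conflict. That stands as far as it goes, and it is why the point ranks low. It does not remove the point: the protocol itself states the summary for a named growth-safety variable, and a better one can be built from data already collected.

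The gap is also partly covered. Cycle 5 Day 1 is a matched comparison in the planned table. Growth plates and Tanner stage are followed, and adverse events are split by age. Loss of alignment after Cycle 5 affects every by-visit safety table, not height alone. All of this stands.

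The sizes are extremes. 44% is the enrolment floor with no adult growth, and 3.25 compares an Arm B completer with an Arm A subject still treated at Cycle 18. Neither is an expected average.

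Three stronger readings are tempting but not supported:
- That percentiles for blood pressure but not for height are a contradiction. The blood pressure percentiles also drive dosing rules; they show only that an age-referenced scale is practical here.
- That the arms cannot be compared on height. They can at Week 12, and later with elapsed-time windows.
- That the protocol prescribes raw centimetres and excludes anything else. It is silent on standardisation.

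**Conclusion.** The point holds as a low-priority improvement. As specified, the height summary pools growing and mostly grown subjects, and after Cycle 5 it does not compare the arms at like times. In the extreme case it shows 44% of an effect in minors, rising to 67% with 48 minors, and the Off-Treatment Visit can differ by a factor of 3.25 in elapsed time. These figures assume no adult growth, an equal share of minors in each arm, no cycle delays and, for the last, an Arm A subject treated through Cycle 18. The documents give no growth rates, so no size in centimetres is claimed. The output is descriptive, and efficacy, sample size and alpha are unaffected.

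**What to change.** In Section 8.7.1.8.4:
- For subjects under 18 at informed consent, add change from baseline in height SDS by arm at Week 12 (Cycle 5 Day 1).
- Where data allow, add windows around Weeks 24, 36 and 48 that combine on-treatment and follow-up heights, with n shown. Count from first dose, the protocol's safety Study Day 1.
- Name the stature-for-age reference, for example CDC. Appendices 8 and 9 hold only BMI charts, although inclusion criterion 10 already draws on CDC stature data. It must cover subjects who turn 18 on study, who stay in the group set at consent.
- Keep raw height change, split at under 18 and 18 or over.
- List or exclude subjects whose standing height is affected by amputation or limb surgery. The dosing section already foresees amputees.

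The cost is a few sentences, one variable derived from age, sex and height, and a reference chart to name. No visit or procedure is added. The drawback is sparse later windows, so Week 12 would carry most of the information.

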#### 8.7.1.8.5 ELECTROCARDIOGRAMS

Descriptive statistics for electrocardiogram parameters (HR, PR, QRS, QT, QTcB, QTcF and RR) and changes from Baseline will be presented by visit. Electrocardiogram (ECG) findings will be summarized. A shift table of worst postbaseline values from Baseline for ECG findings will be provided.

QTc Bazett and QTc Fridericia will be summarized. QTc Bazett and QTc Fridericia will be categorized as both maximum increases from Baseline and maximum postbaseline values.

#### 8.7.1.8.6 OTHER SAFETY ANALYSES

Descriptive summary statistics for LVEF changes from baseline will be calculated and summarized.

The shift of worst postbaseline proteinuria from Baseline will be summarized.

Thyroid-stimulating hormone values will be summarized in 2 categories ( $\leq$ ULN and  $>$ ULN).

Lansky play scores or Karnofsky Performance Status score scores will be summarized by shifts from Baseline to worst postbaseline visit.

Radiographic findings of proximal tibial growth plates will be listed and analyzed if appropriate.

#### 8.7.1.9 Other Analyses

##### 8.7.1.9.1 HEALTH-RELATED QUALITY OF LIFE

Descriptive statistics will be presented for all PedsQL endpoints at each analysis time period by treatment arm. Baseline is defined as the later value of Day -1 or at Cycle 1 Day 1 prior to treatment.

This will be collected at baseline, at C2D1, C3D1, Week 18, C8D1, C18 D1 and at the Off-Treatment Visit. Score change from baseline in PedsQL at each analysis timepoint will be analyzed. Primary timepoint for assessment is at week 18 for all PedsQL endpoints.

Detailed HRQoL analysis plan will be provided in a separate analysis plan and the results will be provided in a stand-alone report.

##### 8.7.1.9.2 PALATABILITY AND ACCEPTABILITY QUESTIONNAIRE

Measurement of palatability will be assessed using the Hedonic scale ([Guinard, 2001](#)) which is a Visual Analog Scale (VAS) in subjects receiving the suspension formulation in the study.

### **8.7.2 Determination of Sample Size**

A binomial-based comparison of 2 proportions using correction for continuity was used for sample size estimation. A total sample size of 72 subjects is estimated to achieve 80% statistical power at 1-sided alpha of 0.1 to detect a difference of 30% based on the assumption that PFS-4m for Arm A (lenvatinib arm) is 55% and for Arm B is 25%. Alpha is the type 1 error probability of declaring lenvatinib arm being effective when the true lenvatinib arm PFS-4m rate is only 25%.

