#### 8.7.1.6.1 PRIMARY EFFICACY ANALYSIS

The primary analysis of PFS-4m rate will be based upon data provided by IIR of tumor assessments. PFS-4m rate and their Greenwood standard errors will be evaluated using the K-M estimates from both treatment groups. The statistical significance of the difference in the 2 K-M PFS-4m rates comparing lenvatinib + chemotherapy agent (Test Arm) vs. chemotherapy agent alone (Control Arm) will be tested using a 2-sided 80% CI. This 2-sided

80% CI and a p-value will be constructed using the difference of these 2 K-M PFS-4m rates and the 2 corresponding Greenwood standard errors. Statistical significance of the difference is declared if the CI is entirely above 0. This is equivalent to a test using a 1-sided test at alpha=0.1. The 2-sided 95% CIs will also be provided for descriptive purposes. PFS-4m rate will also be analyzed using a binomial approach as a sensitivity analysis by excluding subjects whose PFS are censored prior to 18 weeks.

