### **Number of Subjects**

Approximately 72 subjects will be randomised (36 subjects in each arm).

For the primary endpoint (intent-to-treat analysis), at least 32 subjects  $< 18$  years old (at the time of informed consent) will be randomized.

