**Sample Size Rationale**

A binomial-based comparison of 2 proportions using correction for continuity was used for sample size estimation. A total sample size of 72 subjects is estimated to achieve 80% statistical power at 1-sided alpha of 0.1 to detect a difference of 30% based on the assumption that PFS-4m for Arm A (lenvatinib arm) is 55% and for Arm B is 25%. Alpha is the type 1 error probability of declaring lenvatinib arm being effective when the true lenvatinib arm PFS-4m rate is only 25%.

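### The stated 80% power for 72 subjects does not follow from the stated inputs: the continuity-corrected method needs 60 subjects, and 72 give about 87%

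*Protocol*

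**What the plan says.** The sample-size statement stands in Protocol Section 8.7.2 and again in the synopsis under Sample Size Rationale. The method is given as: "A binomial-based comparison of 2 proportions using correction for continuity was used for sample size estimation". The result is given as: "A total sample size of 72 subjects is estimated to achieve 80% statistical power at 1-sided alpha of 0.1". The assumed PFS-4m rates are 55% in Arm A and 25% in Arm B. The synopsis (Number of Subjects) and Section 8.3 fix 36 subjects per arm. Neither statement of the sample size mentions dropout, censoring or any other inflation.

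The primary test is set out in Section 8.7.1.6.1. It is a two-sided 80% confidence interval and a p-value "constructed using the difference of these 2 K-M PFS-4m rates and the 2 corresponding Greenwood standard errors", with success declared if the interval lies above 0. The protocol equates this with a one-sided test at alpha 0.1.

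**The concern.** Section 8.7.2 prints every input to its calculation: both rates, alpha and its sidedness, the power, the method, the total and the allocation. The statement can therefore be checked in full without a statistical analysis plan, and it fails the check. A reader who repeats it obtains a smaller sample size, or a higher power, than the one printed.

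What is at stake is the documentation of the design. The 80% figure will be carried into the study report and used to judge how informative a non-significant result is. At the assumed rates, 80% power means a 20% chance of missing the effect. The stated method at 72 subjects implies about 13% (1 − 0.871). A reader also cannot tell whether 72 is a miscalculation or holds an allowance that was left out of the text.

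**Working it through.** **Inputs (Section 8.7.2; allocation from the synopsis and Section 8.3).** p_A = 0.55, p_B = 0.25, difference 0.30, mean rate 0.40, one-sided alpha 0.1 (z = 1.2816), power 80% (z = 0.8416), 1:1 allocation.

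**Step 1. Sample size by the stated method.** Without continuity correction, per arm:

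n = [1.2816·√(2·0.40·0.60) + 0.8416·√(0.55·0.45 + 0.25·0.75)]² / 0.30²
= [1.2816·√0.48 + 0.8416·√0.435]² / 0.09 = 23.1

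With continuity correction:

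n_c = (23.1/4)·[1 + √(1 + 4/(23.1·0.30))]² = 29.4, so 30 per arm and **60 in total**, against the 72 stated.

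**Step 2. Power at the stated size (36 per arm), same method.**

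z = [0.30 − 1/36 − 1.2816·√(0.48/36)] / √(0.435/36) = (0.3000 − 0.0278 − 0.1480) / 0.1099 = 1.130

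Power = Φ(1.130) = **87.1%**. Exact binomial enumeration of the continuity-corrected test gives 86.3%; Fisher's exact test gives the same. As a check, the formula gives 79.4% at 29 per arm and 80.7% at 30, in agreement with Step 1.

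**Step 3. Attempts to reproduce 72 at 80% power, one-sided 0.1.**

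| Variant | Per arm for 80% | Total |
|---|---|---|
| Pooled variance, continuity correction (as stated) | 30 | 60 |
| Unpooled variance, continuity correction | 29 | 58 |
| Pooled variance, no correction | 24 | 48 |
| Arcsine | 24 | 48 |
| Fisher exact (79.8% at 28, 81.7% at 29) | 29 | 58 |

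None gives 72.

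**Step 4. What an unstated allowance would have to be.** If 60 evaluable subjects were the target, 72 corresponds to a loss of 12/72 = 16.7%. A 20% loss would give 60/0.8 = 75; 72 arises from 20% only as 60 × 1.2.

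**Step 5. The planned test, for context.** With no censoring before 4 months, the Kaplan-Meier/Greenwood comparison reduces to the unpooled test of two proportions without continuity correction. At 36 per arm:

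z = 0.30/0.1099 − 1.2816 = 1.448, power 92.6% by normal approximation and 91.1% by exact enumeration (exact type I error 10.5% at 25% in both arms).

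Early censoring lowers this. The protocol gives no censoring rate, so the following simulation assumes exponential PFS and independent exponential censoring:

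| Assumed probability of censoring by 4 months | Power at one-sided 0.1 |
|---|---|
| 0% | 91% |
| 10% | 91% |
| 20% | 89% |
| 30% | 87% |

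**The case against.** The strongest defence is that 72 may contain a deliberate and legitimate allowance. A reader might infer that this is ruled out because the primary analysis is an intention-to-treat Kaplan-Meier estimate on all randomized subjects. The documents do not support that inference. A subject censored before 4 months stays in the analysis set but contributes less information at 4 months. The protocol foresees such losses: PFS censoring follows the 2007 FDA guidance (Section 8.7.1.6.2), scheduled tumour assessments stop when another anticancer therapy starts (Section 8.5.1.2.1), and a binomial sensitivity analysis excludes subjects censored before 18 weeks (Section 8.7.1.6.1). If 12 of 72 were excluded there, evenly between arms, the 60 left are exactly what the stated method needs. An allowance is therefore plausible, but Section 8.7.2 attributes the 80% to 72 subjects and states no allowance.

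A second defence is that the discrepancy is conservative and leaves the test, the estimate, the error rate and the decision rule as they are. That stands, and it limits the weight of the point.

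A third is that sizing a Kaplan-Meier landmark comparison by a continuity-corrected binomial method is a common simplification, which here errs on the safe side. That also stands. Section 8.7.2 does not claim to give the power of the Greenwood test, so the difference in method is not an error.

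**Conclusion.** The power statement is wrong as written. By the method and inputs in Section 8.7.2, 80% power needs 60 subjects, and 72 give about 87% (86% exact). The excess is 12 subjects, or 6 to 7 points of power. This rests only on figures printed in the protocol. The trial is not underpowered, and no conclusion it could reach is endangered.

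Three stronger readings are not supported:

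- **That the planned test simply has 91% power.** This holds only if nobody is censored before 4 months; with early censoring it is lower.
- **That 72 was derived from a stricter alpha.** The continuity-corrected test at one-sided 0.05 does have 79.9% exact power at 36 per arm. But the protocol states one-sided 0.1 in both the sizing and the analysis sections, and the closed formula at 0.05 gives 39 per arm (78 in total). The coincidence shows nothing about where 72 came from.
- **That the success criterion should move to one-sided 0.05 because there is power to spare.** That would change the primary decision rule and would not repair the arithmetic. The 10% level is openly stated.

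**What to change.** Restate the sample-size text in Section 8.7.2 and in the synopsis (Sample Size Rationale) along these lines: *By a continuity-corrected comparison of two proportions at one-sided alpha 0.1, 60 subjects give 80% power for 55% against 25%; the planned 72 give about 87%.*

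If 72 includes an allowance for subjects censored before 4 months, add its size and basis; 60 evaluable of 72 would be a loss of about 17%. If there was another reason for 72, state that instead.

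If power for the planned Kaplan-Meier/Greenwood test is also quoted, give it as about 91% if no subject is censored before 4 months, and lower with early censoring.

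The cost is wording only. Enrolment, the primary test and the one-sided 0.1 criterion stay as they are.
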